13. ECG

8.2.Treatment Phase

For this study, the following assessments will be performed on Cycle 1, Day 8 (+/- 3 days) of the second agent of each study treatment:

1. Brief update of medical history
2. Physical exam with vital signs, height, body weight, and pulse oximetry
3. Document concomitant medications
4. Collect adverse events
5. Labs: CBC with differential, CMP, magnesium
6. ECOG performance assessment

The following assessments will be performed on a monthly basis, coinciding with Day 1 of each subsequent cycle (+/- 3 days).

1. Brief update of medical history
2. Physical exam with vital signs, height, body weight, and pulse oximetry
3. Document concomitant medications
4. Collect adverse events
5. Labs: CBC with differential, CMP, magnesium
6. ECOG performance status assessment
7. Tumor tissue biopsy for specimen analysis and correlative testing and blood draw for correlative studies around Day 28 of cycle 1 only (+/- 7 days)

The following assessments will be performed on day 15 of each cycle (+/- 3 days), prior to cetuximab infusion:

1. Labs: CMP, magnesium

8.3.Follow-up Phase

Patients will be followed for 5 years from study entry, or until death, whichever occurs first. Patients removed from study for unacceptable adverse events will be followed until resolution or stabilization of the adverse event. Patients taken off study to undergo non-study treatment will be censored as progressive disease as of the date they begin non-protocol therapy. Patients refusing protocol-defined follow-up will be censored as to their status on the day of last contact.

Patients will be seen within 28 days of the last treatment dose. At this visit, the following assessments will be conducted:

1. Brief update of medical history
2. Physical exam with vital signs, height, body weight, and pulse oximetry
3. Labs: CBC with differential, basic metabolic panel, hepatic function panel
4. ECOG performance status assessment

5. Collect adverse events

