12.2.2. Secondary Endpoints

Progression-free survival (PFS), defined as the interval from the date of first dose of study drug (ibrutinib or cetuximab whichever occurs first) to disease progression or death from any cause, whichever occurs first.

Overall survival (OS), defined as the date of first dose of ibrutinib or cetuximab, whichever given first, to the date of death from any cause.

Duration of response is measured from the time measurement criteria are met for complete response or partial response (whichever is recorded first) until the first date that recurrent or progressive disease is objectively documented (taking as reference for progressive disease the smallest measurements recorded since the treatment started) or death of any cause.

Overall frequency and severity of adverse events per CTCAE v4.0.

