12.5. Secondary Efficacy Analysis

Demographic and clinical characteristics of the patients will be summarized using frequency counts and percentages, means and standard deviations or medians and interquartile ranges, as appropriate. Best overall response will be summarized as proportion with 95% confidence intervals. Progression-free survival, overall survival, and duration of response will be described by Kaplan-Meier models to plot these endpoints and estimate median times with a 95% confidence interval. Associations of treatment satisfaction and tolerability with HRQOL will be assessed.

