1. By standard institutional practices. Required only for oropharyngeal and unknown primary tumors
2. Full physical exam at baseline; targeted physical exam at other time points.
3. CBC with Diff: Complete blood count with differential.
4. CMP: Comprehensive metabolic panel (bicarbonate, calcium, chloride, creatinine, glucose, potassium, sodium BUN, albumin, bilirubin total, alkaline phosphatase, total protein, ALT, AST).
5. Pregnancy test for females of child-bearing potential only. Should be obtained with 72 hours of starting therapy and again as indicated
6. Newly obtained tumor tissue collection should be performed when feasible. Otherwise, an archived tumor specimen is adequate.
7. Blood for correlative studies should be collected at the same time blood is drawn for CBC and CMP if possible. 30 ml blood to be collected prior to initiation of study treatment and on cycle 2 day 1 (± 7 days).
8. Imaging for radiographic disease assessment will be performed every 8 weeks (every 2 cycles) following treatment initiation (± 7 days). The same imaging modality should be used throughout the study when feasible. For patients who are clinically stable, a repeat scan will be required 4 weeks (± 7 days) after initial radiographic findings of disease progression as a confirmatory assessment. For CT or MRI, neck and chest should be evaluated; abdomen/pelvis as indicated. If a PET/CT is utilized, CT must be diagnostic quality.
9. Ibrutinib administration will begin 7 days before the start of the second agent and is taken orally on a daily basis.
10. +/- 7 days

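### Section 8.3 censors follow-up refusers at last contact without limiting the rule to any endpoint; applied to PFS and duration of response, it credits progression-free time that no scan supports

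*Combined protocol and SAP*

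**What the plan says.** Section 8.3 (Follow-up Phase) states: "Patients refusing protocol-defined follow-up will be censored as to their status on the day of last contact". The sentence before it deals with other treatment: "Patients taken off study to undergo non-study treatment will be censored as progressive disease as of the date they begin non-protocol therapy". Neither sentence names an endpoint.

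Section 12.2.2 runs PFS "to disease progression or death from any cause, whichever occurs first", overall survival "to the date of death from any cause", and duration of response "until the first date that recurrent or progressive disease is objectively documented" or death. None of the three definitions has a censoring date. Section 12.5 adds only that all three "will be described by Kaplan-Meier models to plot these endpoints and estimate median times with a 95% confidence interval".

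Appendix 1, footnote 8, sets the assessment interval: "Imaging for radiographic disease assessment will be performed every 8 weeks (every 2 cycles) following treatment initiation", with a window of 7 days either way. Section 8.3 follows patients for 5 years or until death, and Appendix 1 has a follow-up column every 2 months after end of treatment.

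**The concern.** The Section 8.3 sentence is the only censoring date in the document for a patient who stops follow-up. A statistician programming PFS from this text has nothing else to use, and nothing confines the rule to survival. The neighbouring sentence speaks of progressive disease, so the paragraph is not plainly about survival alone.

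A telephone call or clinic visit without imaging establishes that a patient is alive. It does not establish that the tumor has not progressed. The protocol makes such contacts likely: Section 9.1 lets patients stop treatment while remaining in follow-up, Section 9.2 asks sites to pursue patients who miss appointments, and the post-treatment visit in Section 8.3 lists no imaging.

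At stake are two descriptive secondary endpoints. Readers are likely to set them beside the protocol's own cetuximab figures: median PFS of 2.4 months or less (Section 1.1.2) and median response duration of 5.8 months (Section 1.5.3). Responders will be few. Rejecting the null needs 5, and a 40% rate gives 0.40 × 18 = 7.2, so one patient can move the duration curve.

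**Working it through.** **Plan figures.** No stated figure depends on the censoring rule. The design figures reproduce:
- early stopping at a 10% response rate: 0.9^12 + 12 × 0.1 × 0.9^11 = 0.659 (plan: 66%);
- exact power at 40% (stop at 1 or fewer of 12, reject at 5 or more of 18): 0.903 (plan: 90%);
- adjusted power by the plan's ratio method: 0.840 (plan: 84%).

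These rest on a response proportion, so the rule cannot alter them.

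**Mechanism.** Suppose a patient has stable disease at the week 8 scan, refuses further scans, and is last contacted at week 26. Last-contact censoring credits 26 − 8 = 18 weeks without assessment and keeps the patient at risk at the week 16 and week 24 steps. With d events among r at risk, including this patient, the Kaplan-Meier factor is 1 − d/r. With last-scan censoring it is 1 − d/(r − 1), which is smaller. For illustration, with r = 7 and d = 2, the factors are 1 − 2/7 = 0.714 and 1 − 2/6 = 0.667. If contact ends before the next scheduled scan, no progression step falls in the gap and the two rules agree, apart from deaths.

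**Size.** Kaplan-Meier simulation with 18 patients and 1,500 runs per setting.
- From the documents: scans every 8 weeks ± 1; median PFS 2.4 months (cetuximab alone) or 5.6 months (platinum-based combination), both from Section 1.1.2.
- Assumed: exponential PFS; 10-30% refuse; refusal starts uniformly over weeks 0-26 and is unrelated to prognosis; 15% of PFS events are deaths.

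26-week PFS, median 2.4 months, shown as complete follow-up / last-scan / last-contact:

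| Refusing | Contact ends at refusal | 0-8 weeks later | 8-26 weeks later |
|---|---|---|---|
| 10% | 0.197 / 0.193 / 0.197 | 0.196 / 0.191 / 0.201 | 0.196 / 0.191 / 0.221 |
| 20% | 0.198 / 0.190 / 0.198 | 0.196 / 0.186 / 0.208 | 0.198 / 0.187 / 0.250 |
| 30% | 0.199 / 0.185 / 0.198 | 0.195 / 0.181 / 0.215 | 0.199 / 0.184 / 0.278 |

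Excess of last-contact over complete follow-up, in points, for 10, 20 and 30% refusing:
- contact ends at refusal: 0.0, 0.0, −0.1;
- 0-8 weeks later: 0.5, 1.2, 2.0;
- 8-26 weeks later: 2.5, 5.2, 7.9.

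With median 5.6 months and 20% refusing, the excess is 0.514 − 0.503 = 1.1 points (0-8 weeks) and 0.540 − 0.503 = 3.7 points (8-26 weeks).

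A simpler model without deaths or scan windows has a true 26-week value of 0.5^(24/10.4) = 0.202, because the last scan before week 26 is at week 24. It gives about 20% under last-scan censoring. Last-contact censoring gives 21-22% (contact up to 8 weeks) and 23-28% (up to 26 weeks).

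**Duration of response.** With 7 responders, median 5.8 months and 20% refusing, the mean Kaplan-Meier median in weeks (complete / last-scan / last-contact) is 31.2 / 30.2 / 31.5 when contact ends at refusal and 31.2 / 30.0 / 36.5 when it ends 8-26 weeks later.

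**Refusal linked to imminent progression.** With large samples, 20% refusing, median 2.4 months and contact 0-8 weeks later, 26-week PFS is 0.199 / 0.208 / 0.234. Both rules are then high, last-contact more so.

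**The case against.** The strongest reply is that the sentence sits in an operational section and its phrase about status does not say how progression status is fixed. A reader might infer that the plan orders last-contact censoring for every endpoint. The text does not say that. It leaves the rule unrestricted and offers no alternative, which is the defect claimed here.

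A reader might also infer that PFS and duration of response will be biased upward in this trial. That does not follow. The bias needs contact to outlast a missed scan, and the documents give neither the number of refusers nor the gap. Section 9.1 treats withdrawal of consent as ending follow-up, so for those patients last contact may fall close to refusal. The preceding sentence of Section 8.3, if read as counting new treatment as progression, pulls the other way for the patients it covers. The net direction is therefore not fixed.

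Last-scan censoring is not exact either. For gaps of 0-8 weeks at 20% refusal its error is 0.186 − 0.196 = −1.0 point, against +1.2 for last contact. This shortfall largely disappears when deaths and the scan window are left out of the simulation. For longer gaps, last-scan censoring is clearly closer.

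Finally, the consequence is limited. No formal comparison with the historical figures is planned, and with 18 patients the standard error of a 20% estimate is √(0.2 × 0.8/18) = 0.094, or about 9 points. That stands. But sampling error is reported in the confidence interval, whereas this bias is not.

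**Conclusion.** The concern holds as a conditional one. The stated rule is unsuitable for PFS and duration of response, and nothing else in the plan displaces it. Under 10-30% refusal unrelated to prognosis and a median PFS of 2.4 months, the excess in 26-week PFS is about 1-2 points when contact lasts up to 8 weeks after refusal and about 2-8 points when it lasts up to 26 weeks. It is essentially zero when last contact comes before the next scheduled scan. Refusal rates and contact gaps are assumptions throughout.

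A reader should not infer that the trial's main conclusion is at risk. The response-rate test, the sample size and the stopping rule do not use this censoring date, and last contact remains appropriate for overall survival.

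**What to change.** In Sections 8.3 and 12.2.2:
- limit last-contact censoring to overall survival;
- for PFS and duration of response, censor patients without documented progression or death at the last evaluable tumor assessment. For PFS, use the first-dose date if there is no assessment after baseline. Responders always have one, so duration of response needs no fallback;
- report last-contact censoring as a sensitivity analysis.

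The cost is a sentence or two of wording and one extra analysis, using scan dates already collected. PFS and duration of response may look slightly less favourable, and last-scan censoring can run about 1 point low. It does not remove bias from refusal that is related to prognosis, so the number of refusers and the gap from last scan to last contact should be reported beside the curves.

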9. SUBJECT WITHDRAWAL

9.1. Withdrawal from Study Treatment

Patients can be taken off the study treatment and/or study at any time at their own request, or they may be withdrawn at the discretion of the investigator for safety, behavioral or administrative reasons. The reason(s) for discontinuation will be documented and may include:

- Patient voluntarily withdraws from treatment (follow-up permitted);
- Patient withdraws consent (termination of treatment and follow-up);
- Patient is unable to comply with protocol requirements;
- Patient demonstrates disease progression (unless continued treatment with study regimen is deemed appropriate at the discretion of the investigator);
- Patient experiences toxicity that makes continuation in the protocol unsafe;
- Treating physician judges continuation on the study would not be in the patient's best interest;
- Patient becomes pregnant (pregnancy to be reported along same timelines as a serious adverse event);
- Development of second malignancy (except for basal cell carcinoma or squamous cell carcinoma of the skin) that requires treatment, which would interfere with this study;
- Lost to follow-up. If a research patient cannot be located to document survival after a period of 2 years, the subject may be considered "lost to follow-up." All attempts to contact the patient during the two years must be documented and approved by the Data Monitoring Committee.

9.2. Withdrawal from Study

Within the provisions of informed consent and good clinical judgement with respect to safety, every attempt should be made to have patients complete the study. The following are reasons to terminate the participation of any patient in the study:

- Intolerable adverse effects
- Gross non-compliance with the protocol
- The patient wishes to withdraw for whatever reason
- Investigator judgement
- The Sponsor elects to end the study, or any portion thereof, for any reason

Although a patient is not obliged to give his/her reason for withdrawing prematurely, the Investigator will make a reasonable effort to obtain the reason while fully respecting the patient's rights. All patients who are enrolled and treated (i.e., receive any amount of study product) will

be included in the safety analyses. Thus, every effort will be made to contact a patient who fails to appear for any follow-up appointments/contacts, in order to ensure that he/she is in satisfactory health.

10. **MEASUREMENT OF EFFECT**

10.1. **Antitumor Effect**

Tumor measurements will be performed on scans. Response and progression will be evaluated in this study using the international criteria proposed by the revised Response Evaluation Criteria in Solid Tumors (RECIST) guideline (version 1.1) [*Eur J Ca* 45:228-247, 2009]. Changes in the largest diameter (unidimensional measurement) of the tumor lesions and the shortest diameter in the case of malignant lymph nodes are used in the RECIST criteria.

10.1.1. **Definitions**

Evaluable for toxicity. All patients will be evaluable for toxicity from time of signed consent until 30 days following last dose of study drug.

Evaluable for objective response. Only those patients who have measurable disease present at baseline, have received at least one cycle of therapy, and have had their disease re-evaluated will be considered evaluable for response. These patients will have their response classified according to the definitions stated below. (Note: Patients who exhibit objective disease progression prior to the end of cycle 2 will also be considered evaluable.)

Evaluable Non-Target Disease Response. Patients who have lesions present at baseline that are evaluable but do not meet the definitions of measurable disease, have received at least one cycle of therapy, and have had their disease re-evaluated will be considered evaluable for non-target disease. The response assessment is based on the presence, absence, or unequivocal progression of the lesions.

10.1.2. **Disease Parameters**

Measurable disease. Measurable lesions are defined as those that can be accurately measured in at least one dimension (longest diameter to be recorded) as ≥ 20 mm by chest x-ray or as ≥ 10 mm with CT scan, MRI, or calipers by clinical exam. All tumor measurements must be recorded in millimeters (or decimal fractions of centimeters).

Note: Tumor lesions that are situated in a previously irradiated area can be considered measurable if there has been documented progression in these lesions following the completion of radiation.

Malignant lymph nodes. To be considered pathologically enlarged and measurable, a lymph node must be ≥ 15 mm in short axis when assessed by CT scan (CT scan slice thickness recommended to be no greater than 5 mm). At baseline and in follow-up, only the short axis will be measured and followed.

Non-measurable disease. All other lesions (or sites of disease), including small lesions (longest diameter < 10 mm or pathological lymph nodes with ≥ 10 to < 15 mm short axis), are considered non-measurable disease. Bone lesions, leptomeningeal disease, ascites, pleural/pericardial effusions, lymphangitis cutis/pulmonitis, inflammatory breast disease, and abdominal masses (not followed by CT or MRI), are considered as non-measurable.

Note: Cystic lesions that meet the criteria for radiographically defined simple cysts should not be considered as malignant lesions (neither measurable nor non-measurable) since they are, by definition, simple cysts.

‘Cystic lesions’ thought to represent cystic metastases can be considered as measurable lesions, if they meet the definition of measurability described above. However, if non-cystic lesions are present in the same patient, these are preferred for selection as target lesions.

Target lesions. All measurable lesions up to a maximum of 2 lesions per organ and 5 lesions in total, representative of all involved organs, should be identified as **target lesions** and recorded and measured at baseline. Target lesions should be selected on the basis of their size (lesions with the longest diameter), be representative of all involved organs, but in addition should be those that lend themselves to reproducible repeated measurements. It may be the case that, on occasion, the largest lesion does not lend itself to reproducible measurement in which circumstance the next largest lesion which can be measured reproducibly should be selected. A sum of the diameters (longest for non-nodal lesions, short axis for nodal lesions) for all target lesions will be calculated and reported as the baseline sum diameters. If lymph nodes are to be included in the sum, then only the short axis is added into the sum. The baseline sum diameters will be used as reference to further characterize any objective tumor regression in the measurable dimension of the disease.

Non-target lesions. All other lesions (or sites of disease) including any measurable lesions over and above the 5 target lesions should be identified as **non-target lesions** and should also be recorded at baseline. Measurements of these lesions are not required, but the presence, absence, or in rare cases unequivocal progression of each should be noted throughout follow-up.

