5.4. Criteria for Permanent Discontinuation of Study Drug

Investigators are encouraged to keep a subject who is experiencing clinical benefit in the study unless significant toxicity puts the subject at risk or routine noncompliance puts the study outcomes at risk. For a complete list of criteria for permanent discontinuation of study treatment, refer to Section 9.2.

An End-of-Treatment Visit (Section 8.3) is required for all subjects except for those subjects who have withdrawn full consent.

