13.4.4. Other Malignancies

All new malignant tumors including solid tumors, skin malignancies and hematologic malignancies will be reported for the duration of study treatment and during any protocol-specified follow-up periods including post-progression follow-up for overall survival. If observed, enter data in the corresponding eCRF.

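### Sections 5.4, 8.3, 9.1 and 9.2 conflict on whether a patient who stops treatment for toxicity stays in survival and progression follow-up

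*Combined protocol and SAP*

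**What the plan says.** Four sections of the protocol bear on this.

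- **Section 9.2 (Withdrawal from Study)** introduces its list with "The following are reasons to terminate the participation of any patient in the study". The list includes intolerable adverse effects, gross non-compliance and investigator judgement.
- **Section 5.4 (Criteria for Permanent Discontinuation of Study Drug)** concerns drug only, yet says: "For a complete list of criteria for permanent discontinuation of study treatment, refer to Section 9.2".
- **Section 9.1 (Withdrawal from Study Treatment)** also has a toxicity item: "Patient experiences toxicity that makes continuation in the protocol unsafe". Its opening sentence covers leaving treatment, the study, or both. One item expressly keeps follow-up: "Patient voluntarily withdraws from treatment (follow-up permitted". One item, withdrawal of consent, expressly ends it. The toxicity item is marked neither way.
- **Section 8.3 (Follow-up Phase)** begins with a general rule: "Patients will be followed for 5 years from study entry, or until death, whichever occurs first". It continues: "Patients removed from study for unacceptable adverse events will be followed until resolution or stabilization of the adverse event".

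Two other places depend on how long a patient is followed. Section 12.2.2 defines overall survival to death from any cause and progression-free survival to progression or death; section 12.5 analyses both by Kaplan-Meier. Section 13.4.4 asks for new malignancies to be reported on treatment and "during any protocol-specified follow-up periods including post-progression follow-up for overall survival".

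**The concern.** Stopping treatment and leaving the study are different events, and the protocol does not keep them apart for toxicity. A site that stops drug for toxicity is sent by 5.4 to a list whose stated effect is to end participation. It then finds in 8.3 a follow-up rule tied to the adverse event and not to the 5-year horizon.

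If a site follows that route, survival and progression status stop being collected when the event settles. In the Kaplan-Meier analyses the patient would be censored near the time of the toxicity. Kaplan-Meier assumes that censored patients have the same outlook as those still followed, and a patient who has just left for intolerable toxicity may well not. Because 13.4.4 ties the reporting of new malignancies to protocol-specified follow-up, that reporting would end early too. For a new combination, these are patients whose later course one would want to know.

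**Working it through.** **The plan's own design figures.** The rule in section 12.3 is to stop if there are at most 1 of 12 responses and to reject if there are at least 5 of 18.

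- Early stopping at a 10% response rate: 0.9^12 + 12 × 0.1 × 0.9^11 = 0.282 + 0.377 = 0.659 (stated: 66%).
- Exact two-stage power at 40%: 0.903 (stated: 90%).

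Both reproduce. The primary analysis set is everyone with at least one dose, so the follow-up wording does not change it. A patient removed early could miss a later response assessment, but stays in the denominator.

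**Two compliant routes for the same patient.**

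| Step | Site A | Site B |
|---|---|---|
| Toxicity stops treatment | 5.4 sends the site to 9.2 | Uses 9.1, headed treatment withdrawal |
| Status | Participation in the study ends | Off treatment, still in study |
| Follow-up rule | Second quoted sentence of 8.3: to resolution or stabilization | First quoted sentence of 8.3: 5 years or death |
| Contacts | End when the event settles | Every 2 months from end of treatment (Appendix 1) |

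Each site can cite the protocol for what it does, and the two deliver different survival data.

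**Is the 5.4 reference simply wrong?** It calls 9.2 the complete list for stopping treatment. Section 9.2 does not contain disease progression, pregnancy or second malignancy; all three are in 9.1. So 9.2 cannot be the complete list, and the section whose heading and content match is 9.1.

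**How the analysis would treat Site A's patient.** Section 8.3 says how to handle patients who start non-study therapy and patients who refuse follow-up. It gives no rule for removal because of toxicity. Censoring at last contact is therefore an inference, though it is what Kaplan-Meier would do with such a record.

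**Size.** Each such patient is 1/18 = 5.6% of the sample. The documents give no rate of stopping for toxicity, so take k patients as an assumption, with k from 1 to 5. Assume also that the other 18 − k have landmark survival S = 50%, and that the k are censored before any death. Kaplan-Meier then reports 50%. The true proportion lies between:

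- lower limit (all k die before the landmark): (18 − k) × 0.5 / 18
- upper limit (all k survive it): [(18 − k) × 0.5 + k] / 18

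| k | Share of patients | Lower | Upper |
|---|---|---|---|
| 1 | 5.6% | 47% | 53% |
| 2 | 11.1% | 44% | 56% |
| 3 | 16.7% | 42% | 58% |
| 4 | 22.2% | 39% | 61% |
| 5 | 27.8% | 36% | 64% |

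For k = 2: 16 × 0.5 / 18 = 8/18 = 44%, and (8 + 2)/18 = 56%. These are extreme bounds, and their width is k/18 whatever S is.

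**The case against.** The strongest reply is that the protocol never says these patients leave the 5-year follow-up. The first quoted sentence of 8.3 has no exception, and the second contains no word that limits it; it can be read as an added duty to follow the event. In 9.1 only withdrawal of consent is marked as ending follow-up. Section 5.4 goes on to require the End-of-Treatment visit of everyone who has not withdrawn full consent. The 2-monthly follow-up column in Appendix 1 shows no toxicity exception in the legible text. Section 9.1 allows a patient to be called lost only after two years of documented attempts to establish survival, and 9.2 says "every effort will be made to contact a patient who fails to appear for any follow-up appointments/contacts".

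Much of this stands. It shows that the lenient reading is available, so a flat statement that toxicity drop-outs lose their follow-up would be an inference. It does not remove the conflict. The 9.2 sentence concerns patients who miss appointments and has a safety purpose; it does not restore follow-up to someone whose participation has been ended. The limited sentence in 8.3 speaks of removal from the study, and 13.4.6 already requires unresolved serious events to be followed after participation ends, so the added-duty reading makes it partly redundant.

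A reader might also infer two wider losses that the documents do not support.

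- **Late harm in general.** Section 13.4.2 ends general adverse-event capture 30 days after the last dose for every patient, and related serious events after that remain reportable with no toxicity exception. There is no 5-year general collection to lose.
- **Scans.** The legible text does not clearly schedule scans after treatment stops without progression for any patient, and part of Appendix 1 is unreadable. A loss specific to toxicity drop-outs cannot be shown.

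**Conclusion.** The point holds as an unresolved conflict among 5.4, 8.3, 9.1 and 9.2, with one plainly wrong cross-reference in 5.4. On the restrictive reading, which a site could reasonably adopt, patients who stop for toxicity would be censored early in the overall and progression-free survival analyses, and their new-malignancy reporting would be shortened. That the censoring is informative is plausible but not shown, and the documents give no basis for its direction.

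Each affected patient is 5.6% of the sample. The table's counts and its 50% survival are assumptions. It would be tempting to read its shares as the fraction of survival data lost; they are shares of patients, who contribute time and possibly events before they leave. The affected analyses are descriptive secondary ones in a single arm. The primary analysis set and the two-stage decision rule are untouched. The wording should be corrected, because survival status not collected at the time may not be recoverable later.

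**What to change.** 1. Reconcile 5.4, 8.3, 9.1 and 9.2 so that stopping treatment and ending study participation are distinct throughout.
2. Correct the reference in 5.4 from 9.2 to 9.1.
3. State in 8.3 and 9.2 that a patient who stops study treatment for any reason other than withdrawal of consent for follow-up remains in the existing 2-monthly follow-up for survival, and for progression as planned for other patients, for 5 years from study entry or until death.
4. State in 8.3 that following an adverse event to resolution or stabilization is in addition to this.

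This settles who is followed. It does not decide which events should stop treatment; where the sections differ on that, the sponsor must reconcile them. The cost is a wording amendment and continued contact with a few patients who are off treatment, using visits that Appendix 1 already provides.
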